3. STUDY PLAN AND PROCEDURES

3.1 Overall study design and flow chart

This Clinical Study Protocol has been subjected to a peer review according to AstraZeneca standard procedures.

This study is designed as a multicentre, open-label, single arm, long-term study involving patients with a history of gastric and/or duodenal ulcers receiving daily NSAID therapy.

A total of 130 patients with a history of gastric and/or duodenal ulcers with ulcer scar confirmed by the esophagogastroduodenoscopy (EGD) performed at screening will receive D20.

The safety of the concomitant use of D961H and NSAID for a long-term period will be assessed. The efficacy of D20 will be also assessed after 52-week oral administration based on the results of the EGD performed at Weeks 4, 12, 24 and 52 after initial administration to verify presence or absence of gastric and/or duodenal ulcers, and to evaluate the severity of gastric and/or duodenal mucosal lesion at Weeks 4, 12, 24 and 52 after initial administration according to modified LANZA score, and investigator's assessment for presence/absence and severity of GI symptoms performed every 4 weeks. If development of gastric and/or duodenal ulcer is observed, the patient will be discontinued from the study.

Findings of EGD including those judged from screening results with an evidence of an ulcer scar and those judged by the investigator(s) after initial administration as gastric and/or duodenal ulcers will be reviewed as needed by the central evaluation committee (see Section 6.7) established by AstraZeneca K.K..

An interim analysis will be performed when 24-week data is locked. The results from this analysis will be submitted to the authority for application for drug approval.

[Table 2](#) shows the study plan including frequency and time of visits.

Table 2 Study Plan

Period	Screening		Study Treatment								
	1	Regis- tration 2	3	4	5	6 7	8	9 10	11	12 13 14	15 or at disc onti nuat ion ^k
Number of weeks before and after Visit 2	2W – 0	0	4W	8W	12W	16W 20W	24W	28W 32W	36W	40W 44W 48W	52W -
Time window	-	-	±4d	±4d	±4d	±4d	±4d	±7d	±7d	±7d	±7d
Informed consent ^a	X										
Inclusion/exclusion criteria	X	X									
Demographic data	X										
Medical/surgical history	X										
Complications	X	X									
Physical examination	X	X	X	X	X	X	X	X	X	X	X
Vital signs	X		X	X	X	X	X	X	X	X	X
Clinical laboratory tests ^{b, c}	X		X	X ^l	X	X ^l	X	X ^l	X	X ^l	X
Pregnancy test (urine) ^d	X										
Hp test (IgG antibody)	X ^m										

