4.6.1 Presence/Absence of gastric and/or duodenal ulcer

4.6.1.1 Methods of assessment

At Visits 1, 3, 5, 8 and 15 (at screening, Weeks 4, 12, 24 and 52 after initial administration), EGD will be performed in the fasting state to confirm presence/absence of gastric and/or

duodenal ulcer based on the following criteria. If gastric and/or duodenal ulcer is present, the site, stage (the Sakita/Miwa classification) and longitudinal diameter of ulcer will be recorded in the eCRF.

Presence/Absence of gastric and/or duodenal ulcer

If gastric and/or duodenal ulcer is verified by EGD and is in the active stage (A1 or A2) or in the healing stage (H1 or H2) according to the Sakita/Miwa classification, “presence of ulcer” should be defined.

Site of ulcers:

Site I: cardia part, fornix, upper gastric corpus, middle gastric corpus, lower gastric corpus, gastric angle, pyloric vestibular part, bulb, retrobulbar region

Site II: anterior wall, posterior wall, greater curvature, lesser curvature

Stage (Sakita/Miwa classification)

Active stage:

A1: Slough in the ulcer is thick with inflammatory swelling in the marginal area.

A2: Circumferential white ring and hyperemia are seen in the marginal area of the ulcer.

Healing stage:

H1: The ulcer is shrunk with redness in the marginal area, and mucosal plicae are gathering.

H2: The ulcer is further healed and upheaved, being covered with thin slough

Scar stage:

S1: so-called ‘Red Scar’: Hyperemia still remains in the centre of the scar.

S2: so-called ‘White Scar’: Hyperemia in the scar disappears, turning into the same colour as adjacent mucosa.

The longitudinal diameter

The longitudinal diameter will be measured referring such as endoscopy forceps. If several ulcers are found, record the longitudinal diameter of the largest ulcer.

EGD images

For the central review of confirmation about presence/absence of gastric and/or duodenal ulcer, EGD images showing the sites judged to be the scar of ulcers at screening and the sites

judged to be the ulcers during the treatment period with the investigational product (one each of close and distant views. The same is required for EGD images in the past used for a lesion with unclear scar) will be submitted to AstraZeneca K.K.. The personal information (such as the name and the medical record number) which can specify the patient should be masked before submission to AstraZeneca K.K..

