6.4.2.1 Gastric and/or duodenal ulcer free status

The following two methods will be used to calculate each proportion of subjects without gastric and/or duodenal ulcer (ulcer-free rate) in FAS and PPS. The population excluding subjects who are declared not to have an ulcer scar by the central evaluation committee at baseline will be evaluated (see Section 6.7). In this analysis, the evaluation of the central committee for the presence/absence of gastric and/or duodenal ulcer after dosing will be used.

[Ulcer-free rate by the Kaplan-Meier method]

It will be defined as an event if gastric and/or duodenal ulcer is observed by EGD and the plots to show the period from the date of initial administration to the date of event occurred will be constructed using the Kaplan-Meier method. Data obtained from the subjects who have not developed ulcer throughout the study period will be cut off on the day of the last test with EGD. Ulcer free rates of gastric and/or and duodenal ulcer at Week 4, 12, 24 and 52 and its 95% confidence intervals will be calculated by the constructed Kaplan-Meier plots.

[Ulcer-free rate by EGD performed at each measurement]

Subjects who remained gastric and/or duodenal ulcer-free status confirmed by the EGD at Weeks 4, 12, 24 and 52 after the initial administration or those who discontinued the study by reason that gastric and/or duodenal ulcer-free status was confirmed before performing the EGD at each measurement will be considered as ulcer-free subjects and the proportion of the ulcer-free subjects will be calculated against the entire number of the subjects included in the

analysis population, and its 95% confidence intervals will be calculated. The proportion of the ulcer-free subjects will be stratified by the following factors to calculate the percentages for each subgroup.

- Sex (Male, Female)
- Age (<65, 65-74, 75≤)
- Hp positive/negative
- Number of types of NSAID (one or more types)
- Use of steroidal agent(s) (Yes or No)
- Genotypes of CYP2C19 (homo EM, hetero EM, PM)
- Underlying diseases (e.g., osteoarthritis, rheumatoid arthritis, lumbago)
- Degree of gastric mucosa atrophy (positive or negative)
Positive: Concentration of pepsinogen I is 70.0 ng/mL or below and pepsinogen I/II is 3.0 or below
Negative: Concentration of pepsinogen I is 70.1 ng/mL or above or pepsinogen I/II is 3.1 or above
- Extension of gastric mucosa atrophy (no atrophy, C-1, C-2, C-3, O-1, O-2, O-3)

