6.5 Determination of sample size

'The Size of Population and Treatment Period to Assess Safety at Clinical Study Phase for Drugs Intended for Long-Term Treatment of Non-life-threatening Conditions' (PMSB Notification No.592 dated 24 May 1995), which reflects ICH E1 guideline mentions that safety data of at least 300 subjects with 6-month treatment need to be included in submission data for new drug application, and that safety data of 100 subjects with 1-year treatment will be ultimately needed. The safety data of subjects receiving D961H 20 mg once daily for 6 months are planned to include data of approximate 155 subjects from ongoing Phase III study and 180 from a clinical study of maintenance treatment in subjects with gastroesophageal reflux disease. Therefore, 130 patients will be enrolled in this study to collect safety data of 100 or more subjects with 1-year treatment considering the discontinuation or the withdrawal from the study.

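### Kaplan-Meier ulcer-free rates use actual EGD dates but are read at nominal weeks, which modestly overstates them and makes the curve after Day 364 an artefact

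*Protocol*

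**What the plan says.** Protocol section 6.4.2.1 fixes all parts of the Kaplan-Meier rule.

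- Event: "It will be defined as an event if gastric and/or duodenal ulcer is observed by EGD".
- Time scale: "the period from the date of initial administration to the date of event occurred".
- Censoring: a subject who stays ulcer-free "will be cut off on the day of the last test with EGD".
- Read-off: "Ulcer free rates of gastric and/or and duodenal ulcer at Week 4, 12, 24 and 52", with 95% confidence intervals, from the resulting curve.

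Section 4.6.1.1 schedules EGD "At Visits 1, 3, 5, 8 and 15 (at screening, Weeks 4, 12, 24 and 52 after initial administration"), and at no other visit. The window row of Table 2 (section 3.1) reads "Time window - - ±4d ±4d ±4d ±4d ±4d ±7d ±7d ±7d ±7d", which is ±4 days up to Week 24 and ±7 days from Week 28 to Week 52. The protocol nowhere maps an EGD date to its nominal visit for this analysis.

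Section 6.4.2.1 also plans a second ulcer-free rate, a proportion by EGD visit with its own confidence interval and all the subgroup breakdowns. Section 6.6 adds an analysis of the data up to Week 24 for the approval application.

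**The concern.** The ulcer is an event that can be seen only when someone looks, and everyone is looked at on four occasions. Treating the day of looking as an exact event time, and reading the curve at the nominal week, does two things.

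First, an ulcer found on Days 29 to 32 at a visit that is on time by Table 2 is not in the Week 4 rate. The same holds after Days 84, 168 and 364.

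Second, at the last EGD a clean subject is censored on the day seen. Those seen early in the window leave the risk set while ulcers are still being recorded in those seen later. The remaining ulcers are divided by a shrinking number, although nobody's risk has changed.

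At stake are the accuracy of the reported ulcer-free rates, which err in one direction, and the shape of the plotted curve, which is itself a planned output.

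**Working it through.** **Inputs.** From the protocol: the EGD schedule and windows above; section 6.5, "130 patients will be enrolled in this study to collect safety data of 100 or more subjects with 1-year treatment", which implies a loss of 1 − 100/130 = 23%; Table 1, six-month ulcer incidence on the 20 mg dose of 5.2% and 5.3%. Weeks 4, 12, 24 and 52 are taken as Days 28, 84, 168 and 364. The protocol gives no figure for the Kaplan-Meier rates, so there is none to reproduce.

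**Assumptions, not in the protocol.** Visit days uniform over the window; 23% cumulative dropout; all ulcers found at scheduled EGDs; Week 52 incidence of 8%, 10.3% or, as a high case, 18% (with 10% at Week 24).

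**Step 1: share of EGDs after the nominal day.**
- ±4 days is 9 possible days, 4 of them late: 4/9 = 44%.
- ±7 days is 15 possible days, 7 of them late: 7/15 = 47%.

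**Step 2: the last interval in closed form.** Let p be the probability of an ulcer at the Week 52 EGD. On day j of the 15-day window, 1/15 of subjects are seen and (16 − j)/15 are still at risk, so the hazard recorded that day is p/(16 − j). The correct total is about p.
- By Day 364 (j = 8): p × (1/15 + … + 1/8) = 0.73p.
- By Day 371 (j = 15): p × (1/15 + … + 1/1) = 3.32p.

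Only 8/15 = 53% of the ulcers are in by Day 364, but the shrinking denominator brings the recorded hazard up to 73%. The two faults partly cancel at the planned read-off and compound after it.

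Hand check for the 10.3% case: p = 1 − 0.897/0.947 = 0.0528. The simulated curve stands at 0.945 once the Week 24 window has closed. Then 0.945 × exp(−0.73 × 0.0528) = 0.909 at Day 364, and 0.945 × exp(−3.32 × 0.0528) = 0.793 at Day 371.

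**Step 3: simulation** (3000 trials, N = 130, the rule of section 6.4.2.1 applied as written).

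| Case (incidence at Week 24 / 52) | Rate (%) | Week 4 | Week 12 | Week 24 | Week 52 | End of curve |
|---|---|---|---|---|---|---|
| 5.3% / 8% | true | 98.0 | 96.5 | 94.7 | 92.0 | 92.0 |
| | as planned | 98.9 | 97.1 | 95.3 | 92.6 | 85.6 |
| 5.3% / 10.3% | true | 99.0 | 97.2 | 94.7 | 89.7 | 89.7 |
| | as planned | 99.5 | 98.0 | 95.7 | 90.9 | 79.2 |
| 10% / 18% | true | 97.0 | 94.0 | 90.0 | 82.0 | 82.0 |
| | as planned | 98.4 | 95.3 | 91.6 | 84.1 | 66.4 |

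The standard error at Week 52 is 2.6 to 3.8 points. With each EGD assigned to its nominal visit, the same estimator returns the true value in all three cases to within 0.1 point. I repeated the simulation with independent code and obtained the same planned and end-of-curve values to within about 0.5 point.

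**Step 4: the 24-week analysis.** With data only to Week 24, that EGD is the last one, so the tail effect moves there. By the same argument over 9 days, the last interval's hazard counts 1/9 + … + 1/5 = 0.75-fold at Day 168 and 1/9 + … + 1/1 = 2.83-fold at Day 172. In the 5.3% / 10.3% case (true 94.7%) the 24-week analysis reads about 95.2% at Day 168 and its curve ends near 90%. The final analysis reads 95.7% at Day 168. The same Week 24 EGDs thus give two different Week 24 rates, because of the censoring rule alone.

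**The case against.** The strongest reply has four parts.

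**The planned figures barely move.** This stands. The Week 52 error is below one standard error, and about 50 to 60 subjects are still at risk on Day 364. A reader who looks at the end of the curve might infer that the Week 52 rate is grossly wrong, or that ulcer incidence is doubled. The documents do not support that: section 6.4.2.1 asks for Week 52 and never for Day 371. Nor are late ulcers at Weeks 4 to 24 lost, since they count in the next rate.

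**The endpoint carries no decision.** This also stands. Safety is primary, efficacy is secondary, no hypothesis is tested, and no efficacy rate is named as the main one.

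**A visit-based rate is already planned.** It does not depend on the day within the window and is a real safeguard. It is only partial, because as worded it appears to count subjects who left while ulcer-free as ulcer-free over the full denominator. With up to 30 of 130 losses allowed for, that leans upward too. Kaplan-Meier is the planned estimate that allows for dropout.

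**Visit mapping belongs in the SAP.** This would hold if the protocol were silent. Here it states the event date, the censoring date and the read-off weeks, and following them as written gives the error. It is true that the protocol does not say which day counts as Week 52; reading it as Day 364 is the natural reading, not a stated one.

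**Conclusion.** The point holds as a modest, systematic error in a stated rule. The planned Kaplan-Meier ulcer-free rates are overstated by about 0.5 to 2 points, and at Week 52 the error is smaller than sampling error. The curve beyond Day 364 should not be interpreted: it ends near 79% for a true 89.7%. The same effect reaches Week 24 in the analysis for the application.

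The sizes rest on uniform visit days, about 23% dropout and the assumed incidences. If visits cluster on or before the nominal day, fewer ulcers are left out at Weeks 4 to 24 and the error there shrinks. With clustering around the nominal day, the Week 52 figure in the middle case was 90.3% to 90.8% in different runs, against 90.9% with uniform days. The direction does not depend on these choices as long as some in-window visits fall late.

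It is worth correcting because the correction is almost free. It is not a must-fix: nothing in the documents makes a decision depend on this rate.

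**What to change.** In section 6.4.2.1, or in the SAP with a reference back to it:

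1. Assign every EGD result, event or censoring, to its scheduled visit (Week 4, 12, 24 or 52) before running Kaplan-Meier, with events ahead of censorings at the same visit.
2. Assign an ulcer found at an unscheduled or discontinuation EGD to the next scheduled visit. Censor a clean discontinuation EGD at the last scheduled visit completed.
3. Apply the same rule to the 24-week analysis, so that the two Week 24 rates are built alike.
4. If wanted, add an interval-censored estimator as a sensitivity analysis. It is not strictly equivalent: for a subject examined after Day 364 the interval spans Day 364, so the Week 52 value is not directly identified.

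Moving the read-off to the end of the window is not a substitute. In the final analysis it works for Weeks 4 to 24, but at Week 52 it picks up the artefact in full.

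The cost is a few sentences and a few lines of programming, with no new data. The curve becomes a step function by visit and loses the exact dates. Rule 2 treats ulcers and clean results off schedule differently, so the number of such subjects should be reported.

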The study is a multicentre, open-label, single arm, long term study involving patients with a history of gastric and/or duodenal ulcers receiving daily NSAID therapy.

Target subject population

Patients aged 20 years and above with a history of gastric and/or duodenal ulcers (diagnosed having osteoarthritis, rheumatoid arthritis, lumbago, etc.) who are receiving daily NSAID therapy.

Test product, dosage and mode of administration

In this study the following test products will be used:

- D961H 20 mg-capsules

Patients will receive one D961H 20 mg capsule once daily orally after breakfast for 52 weeks.

Comparator, dosage and mode of administration

In this study any comparator will not be used.

Duration of treatment

52 weeks

Outcome variables

- **Safety**
 - **Primary outcome variables:**
 - AEs
 - Clinical laboratory values
 - Vital signs
- **Efficacy**
 - **Secondary outcome variables:**

- Presence or absence of gastric and/or duodenal ulcers at Weeks 4, 12, 24 and 52 after initial administration
- Severity of gastric mucosal lesion by modified LANZA score at Weeks 4, 12, 24 and 52 after initial administration
- Presence/absence and severity of NSAID-associated gastrointestinal (GI) symptoms assessed by investigator(s) every 4 weeks from Week 4 to Week 52 after initial administration

Statistical methods

In this study, no hypothesis will be tested.

For safety variables, quantitative data will be summarised using descriptive statistics and qualitative data will be summarised using a frequency table.

For gastric and/or duodenal ulcer free status, ulcer-free rates of gastric and/or duodenal ulcer at Week 4, 12, 24 and 52 and their 95% confidence intervals will be calculated by Kaplan-Meier Method. Also, ulcer-free rates based on EGD results of each measurement and its 95% confidence intervals will be calculated. Modified LANZA scores will be summarised for each measurement using descriptive statistics, and descriptive statistics of the changes from baseline will also be summarised. Presence/absence and severity of NSAID-associated GI symptoms will be summarised using a frequency table.

Since results from this study will be submitted for application for drug approval, interim analysis will be performed when 24-week data are locked.

TABLE OF CONTENTS	PAGE
TITLE PAGE	1
PROTOCOL SYNOPSIS.....	2
TABLE OF CONTENTS.....	5
LIST OF ABBREVIATIONS AND DEFINITION OF TERMS	9
1. INTRODUCTION	11
1.1 Background.....	11

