6. STATISTICAL METHODS AND DETERMINATION OF SAMPLE SIZE

6.1 Statistical evaluation – general aspects

A comprehensive Statistical Analysis Plan (SAP) will be prepared before the database lock.

Only descriptive analysis will be used in this study.

All statistical analyses in this study will be performed by Statistics and Programming Department of AstraZeneca K.K. using the SAS software.

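### A Kaplan-Meier interval for the ulcer-free rate has no width before the first ulcer, which is a realistic outcome at Week 4 (minor)

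*Protocol*

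**What the plan says.** Section 6.4.2.1 plans two ulcer-free rates, each in the full analysis set and the per-protocol set, after removing subjects whom the central committee finds to have no ulcer scar at baseline.

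- **Kaplan-Meier rate.** The section lists "Ulcer free rates of gastric and/or and duodenal ulcer at Week 4, 12, 24 and 52" and then says that "95% confidence intervals will be calculated by the constructed Kaplan-Meier plots". The statistical methods part of the synopsis puts it as "their 95% confidence intervals will be calculated by Kaplan-Meier Method". No variance formula, transformation or rule for a time point without events is given.
- **Visit-based rate.** Ulcer-free subjects at each EGD are divided by the whole "analysis population, and its 95% confidence intervals will be calculated". The method for this interval is not named either.

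The synopsis states that "In this study, no hypothesis will be tested" and section 6.1 that "Only descriptive analysis will be used in this study". Section 6.1 also names SAS as the software and announces a separate SAP, which is not at hand.

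**The concern.** The protocol ties the interval to the Kaplan-Meier curve at four fixed weeks, the first of them early. The intervals in common use with that curve (linear, log, log-log) all take their spread from the Greenwood sum. Before the first event that sum is empty. The linear and log intervals are then 100%-100%, and the log-log interval cannot be computed because it divides by the logarithm of 1. Choosing among the three in the SAP does not remove the problem.

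At stake is a report that shows either complete certainty of prevention at Week 4 or no interval at all. The error would favour the product, in a single-arm study whose 24-week data go into the application for approval (section 6.6).

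**Working it through.** **What can be reproduced.** The plan states no expected ulcer-free rate and no target precision. Section 6.5 says "130 patients will be enrolled in this study to collect safety data of 100 or more subjects with 1-year treatment". That implies a loss of 1 - 100/130 = 23.1%. It is a safety-exposure count and does not depend on this interval.

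**Inputs**
- n = 130 (section 6.5). I also use n = 100, because section 6.4.2.1 removes subjects and repeats the analysis in the per-protocol set.
- Six-month ulcer incidence on 20 mg: 5.2% and 5.3% (section 1.2, Table 1). Placebo: 12.3% and 20.4%.
- Assumptions, not in the documents: constant hazard; six months equals 24 weeks (26 weeks as a check); no censoring before Week 4; every Week 4 EGD counts at Week 4. The 24-week risks of 7.5%, 10% and 13.8% below are assumed values to show the range.

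**Step 1: variance.** With no censoring before Week 4, the Kaplan-Meier estimate is p = 1 - x/n and the Greenwood variance is p(1 - p)/n. At x = 0 this is 0.

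**Step 2: chance of no ulcer by Week 4.** The Week 4 risk is q4 = 1 - (1 - q24)^(4/24), and P(0) = (1 - q4)^n.

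For q24 = 5.3%: q4 = 1 - 0.947^(1/6) = 0.90%, expected ulcers 130 × 0.0090 = 1.2, P(0) = 0.947^(130/6) = 0.307.

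| 24-week risk | n | q4 | P(0) |
|---|---|---|---|
| 5.3% | 130 | 0.90% | 31% |
| 5.3% | 100 | 0.90% | 40% |
| 7.5% | 130 | 1.29% | 18% |
| 10% | 130 | 1.74% | 10% |
| 13.8% | 130 | 2.44% | 4% |

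With six months as 26 weeks and n = 130, 5.3% gives 0.947^20 = 34%. The two placebo rates give 0.877^20 = 7% and 0.796^20 = 1%.

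**Step 3: what would be shown at 0 of 130.** Kaplan-Meier: 100%-100%, or missing. The Clopper-Pearson lower limit is 0.025^(1/130) = 97.2%.

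**Step 4: coverage at Week 4** (q4 = 0.90%, n = 130, exact binomial sum, a zero-event interval counted as a miss). Linear 69%, log-log 66%, Clopper-Pearson 99%. Nearly all of the shortfall is the zero-event case: given at least one ulcer, coverage is 69.1/69.3 = 99.8% (linear) and 66.2/69.3 = 95.5% (log-log).

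**Step 5: later weeks** (5.3% by 24 weeks, n = 130, dropout ignored). P(0) = 0.947^(130 × w/24): Week 12, 0.947^65 = 2.9%; Week 24, 0.947^130 = 0.08%; Week 52, about 0. On the 26-week reading these are 3.8%, 0.15% and about 0. A simulation on that reading with 23% yearly dropout gave about 5%, 0.1% and 0.

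**The case against.** The strongest reply is that the protocol does not prescribe a Greenwood interval. It names only the curve, and variance formulas are ordinary SAP material. The beta product procedure is itself built on the Kaplan-Meier curve, so a SAP could adopt it without contradicting section 6.4.2.1. This stands in part: the SAP can settle the matter. But the text points to the standard intervals, and following it in the usual way fails at a time point without events whichever of them is picked. That is more than an unstated detail.

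A reader might infer several stronger things that the documents do not support:

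- **That the Kaplan-Meier intervals in general cover far below 95%.** The collapse is essentially confined to Week 4 and needs a low early rate, which the documents do not give. Table 1 comes from overseas subjects with an ulcer history or aged over 60. Here all subjects have an ulcer history, so the rate may be higher. At a 24-week risk of 13.8%, log-log coverage at Week 4 is 92%.
- **That few ulcers are as harmful as none.** Given at least one ulcer, log-log coverage in the main scenario is 95.5%. A fallback for, say, fewer than five ulcers is not needed on these figures. The linear interval can still run low later (91% at a 5.3% risk), but that is a choice of transformation, properly left to the SAP.
- **That this interval is the study's only efficacy statement.** The visit-based proportion has its own interval, and the modified LANZA score and GI symptoms are also planned. The visit-based interval would be a safeguard if it were exact, but its method is unnamed.

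**Conclusion.** The point holds for any time point reached before the first ulcer, in practice Week 4. Under a constant hazard and Table 1's 5.3%, about three trials in ten with 130 subjects would reach Week 4 with no ulcer (four in ten with 100). They would then report 100%-100% or nothing in place of a lower limit of 97.2%. If the 24-week risk were 13.8%, this would happen in one trial in 25. The size rests on the assumed Week 4 rate; the zero width itself does not.

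Severity is minor. The estimate is secondary and descriptive, no decision rule uses it, the gap in the lower limit is under three percentage points, and neither the sample size nor the Week 24 and Week 52 results depend on it.

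**What to change.** In section 6.4.2.1 and the synopsis, or in the SAP, keep the Kaplan-Meier estimate and add one of two rules:

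1. At any time point with no ulcer so far, report the exact (Clopper-Pearson) lower limit on the number examined, with 100% as the upper limit.
2. Use the beta product confidence procedure at all four weeks.

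Also name an exact interval for the visit-based proportion.

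Under rule 1 the zero-event trials of the main scenario become hits, since the true 99.1% lies above 97.2%. Log-log coverage at Week 4 rises from 66.2% to 66.2% + 30.7% = 96.9%. The cost is one sentence and a few lines of code. The exact interval is slightly conservative: Clopper-Pearson covers about 97-99% over the Week 4 rates tried.

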3.3.5 Discontinuation of subjects from study treatment or assessment

3.3.5.1 Criteria for discontinuation

Subjects may be discontinued from study treatment and assessments at any time.

Specific reasons for discontinuing a subject from this study are:

- Voluntary discontinuation by the subject who is at any time free to discontinue his/her participation in the study, without prejudice to further treatment
- Safety reasons as judged as the patient to be discontinued by the investigator(s) and/or AstraZeneca K.K.
- Severe non-compliance to protocol as judged by the investigator(s) and/or AstraZeneca K.K.
- Incorrect enrolment i.e., the subject does not meet the required inclusion/exclusion criteria for the study
- Subject lost to follow-up
- Occurrence of an event in conflict of exclusion criteria (e.g., pregnancy)
- Development of gastric and/or duodenal ulcer
- Difficulty to conduct the study as judged by the investigator(s) due to the presence of gastric and/or duodenal mucosal lesion such as bleeding.
- Permanently stopping treatment with daily NSAID
- Others as judged appropriate by the investigator(s) (reasons for discontinuation must be recorded in eCRF)

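### The visit-based ulcer-free rate depends on attrition and on whether an exit endoscopy was done, and all nine subgroup results rest on it alone

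*Protocol*

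**What the plan says.** Protocol Section 6.4.2.1 defines two estimators, both for the full analysis set and the per-protocol set.

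- **Kaplan-Meier.** The event is an ulcer seen at EGD. For the others the rule is "Data obtained from the subjects who have not developed ulcer throughout the study period will be cut off on the day of the last test"; that is, they are censored at their final endoscopy. Rates with 95% confidence intervals are read off at Weeks 4, 12, 24 and 52.
- **Visit-based rate.** Two groups are successes. The first is "Subjects who remained gastric and/or duodenal ulcer-free status confirmed by the EGD at Weeks 4, 12, 24 and 52 after the initial administration". The second is subjects who discontinued and whose "ulcer-free status was confirmed before performing the EGD at each measurement will be considered as ulcer-free subjects". The denominator is the whole analysis population, whoever was examined at the visit.

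The subgroup sentence stands under the visit-based method only: "The proportion of the ulcer-free subjects will be stratified by the following factors to calculate the percentages for each subgroup". Nine factors follow: sex, age, Hp status, number of NSAID types, steroid use, CYP2C19 genotype, underlying disease, pepsinogen-defined atrophy, and endoscopic extent of atrophy. No Kaplan-Meier analysis by subgroup is stated.

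Three other places bear on the point. Section 6.5 says that "130 patients will be enrolled in this study to collect safety data of 100 or more subjects with 1-year treatment"; the margin of 30 is there to cover early leavers. Footnote k to Table 2 asks for the Week 52 tests at early discontinuation only as far as possible, so an exit EGD is not assured. Section 3.3.5.1 lists, separately from ulcer, the withdrawal reason "Difficulty to conduct the study as judged by the investigator(s) due to the presence of gastric and/or duodenal mucosal lesion such as bleeding".

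**The concern.** Once a subject has left with ulcer-free status confirmed, no later ulcer can count, yet that subject stays in the numerator and denominator at every later measurement. A subject with a clean Week 4 EGD who leaves at Week 5 is reported as ulcer-free at Week 52. A leaver whose status was never confirmed stays in the denominator and is not a success. The rate therefore mixes ulcer risk with two things that are not efficacy: how many subjects leave, and whether they were examined before leaving.

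For the overall rate the Kaplan-Meier estimate stands beside it. For the subgroups nothing does, although the protocol gives them a purpose: Section 3.2.1 wants to examine the influence of CYP2C19 genotype and to confirm efficacy in subjects with hypochlorhydria. If dropout differs between the levels of a factor, the percentages can differ with no difference in ulcer risk.

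The sentence also needs rewording on its own account. Read literally, it makes ulcer-free status the reason for discontinuing, which is not a reason in Section 3.3.5.1, and it does not say which EGD confirms the status.

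**Working it through.** **Inputs from the protocol.** 130 enrolled and 100 with one year of treatment (Section 6.5). 6-month ulcer incidence on 20 mg of 5.2% and 5.3%, and on placebo of 12.3% and 20.4% (Table 1, overseas studies). EGD at Weeks 4, 12, 24 and 52.

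**Assumptions.** Constant ulcer hazard h, constant dropout hazard c, dropout unrelated to ulcer risk unless stated, and N = 130 as the analysis population. The protocol gives no dropout rate. An incidence of 10% is added as an intermediate value.

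**Plan's own figure.** The implied loss is 30/130 = 23.1%. With 23%, 100/(1 - 0.23) = 129.9, so 130. This is only a consistency check, because the rate is back-calculated. The protocol states no expected ulcer-free rate to reproduce.

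**Step 1, true Week 52 rate.** h = -ln(0.948)/26 = 0.002054 per week. S = exp(-52h) = 0.948² = 89.9%. Kaplan-Meier targets this value under independent dropout.

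**Step 2, visit-based rate if every leaver has an exit EGD.** c = -ln(100/130)/52 = 0.005045 per week; retention G = 0.7692.
- Still in and ulcer-free at Week 52: S × G = 0.8987 × 0.7692 = 0.6913.
- Left ulcer-free: c/(h + c) × (1 - SG) = 0.7107 × 0.3087 = 0.2194, or 28.5 of 130.
- Rate: 0.6913 + 0.2194 = 91.1%, **+1.2 points**. Ulcers counted: 130 × 0.0893 = 11.6, against 130 × 0.1013 = 13.2 expected.

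At 10% and 30% dropout the excess is +0.5 and +1.6 points.

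**Step 3, the same rate if no leaver has an exit EGD.** Confirmation then comes from the last scheduled EGD. Those who leave before Week 4 are unconfirmed (about 2.6 ulcer-free subjects of 130) and are not successes. Later leavers are successes if clean at their last visit:
- Left in Weeks 4–12: 0.9918 × (0.9800 - 0.9413) = 0.0384
- Left in Weeks 12–24: 0.9757 × (0.9413 - 0.8860) = 0.0540
- Left in Weeks 24–52: 0.9519 × (0.8860 - 0.7692) = 0.1111
- Rate: 0.6913 + 0.2035 = 89.5%, **-0.4 points**.

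**Step 4, higher incidence, 23.1% dropout, same formulas.**

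| 6-month incidence | True | Rule, all exit EGDs | Rule, no exit EGDs |
|---|---|---|---|
| 5.2% | 89.9% | 91.1% (+1.2) | 89.5% (-0.4) |
| 10% (assumed) | 81.0% | 83.2% (+2.2) | 82.0% (+1.0) |
| 20.4% (placebo) | 63.4% | 67.5% (+4.1) | 66.9% (+3.6) |

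**Step 5, informative dropout.** If the ulcer hazard doubles after leaving, and all leavers have an exit EGD, the excess over the true rate is +2.3, +4.1 and +7.1 points for the three incidences. Kaplan-Meier does not remove all of this: at 5.2% it still gives 89.9% against a true 88.8%.

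**Step 6, subgroups.** With exit EGDs, the rule gives SG + (1 - SG) × ln G/(ln S + ln G). Take two subgroups with the same true rate of 80% (illustrative).
- 10% dropout: 0.72 + 0.28 × 0.3207 = 81.0%.
- 40% dropout: 0.48 + 0.52 × 0.6960 = 84.2%.

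The 3.2-point gap comes from attrition alone. At S = 89.9% the same dropouts give 90.4% and 92.0%.

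**Step 7, a tempting alternative denominator.** Subjects examined at Week 52 plus those with an earlier ulcer: 0.6913/(0.6913 + 0.0893) = 88.6%, that is -1.3 points. It drops ulcer-free leavers but keeps the ulcers found before exit.

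**The case against.** The strongest reply is that little depends on this rate. Section 6.1 limits the study to descriptive analysis, the primary objective is safety, and the sample size rests on exposure. Kaplan-Meier is listed first, with intervals at all four time points, so a reader can compare the two overall rates. A shift of 1.2 points is small against a 95% half-width of 1.96 × √(0.911 × 0.089/130) = 4.9 points. In the subgroups, about 12 counted ulcers spread over as many as seven levels leave sampling error far larger than the bias, and nothing in the protocol says that dropout will differ between them. All of this stands, and it limits the severity. It does not give the subgroup percentages a companion estimate that handles leavers differently.

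Two stronger readings are tempting and do not hold.

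- A reader might infer that the Week 52 rate is simply one minus ulcers seen over N, and so is always too high. The text counts only leavers whose status was confirmed; the others count against the rate. At the 5.2% incidence this can reverse the sign (Step 3). The larger upward figures need incidences above those in Table 1 for this dose; 20.4% is a placebo rate.
- A reader might infer that withdrawal for a bleeding non-ulcer lesion misclassifies the endpoint. It does not: the endpoint is ulcer in the active or healing stage (Section 4.6.1.1). Erosions and haemorrhage go to the modified LANZA score, and findings that lead to withdrawal for reasons other than ulcer are recorded as adverse events (Section 4.7.1.2). Only carrying such a subject forward to Week 52 is open to criticism.

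**Conclusion.** The point holds as one about an estimator that depends on attrition and exit-EGD practice. For the overall Week 52 rate the shift is about -0.4 to +1.2 points at the protocol's own incidence and about 23% dropout, and +2 to +4 points at 6-month incidences of 10% to 20.4% if leavers have an exit EGD. These sizes rest on constant hazards, a back-calculated dropout rate and overseas incidences.

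The main consequence lies in the nine subgroup analyses, which have no Kaplan-Meier counterpart and can show differences created by dropout. That is a possibility, not a prediction: the documents do not show that dropout will differ by subgroup. Because the analysis is secondary and descriptive, the severity is minor to moderate; the documents do not support calling it a flaw that invalidates the efficacy results.

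**What to change.** In Section 6.4.2.1:

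1. Report the ulcer-free rate in every subgroup, with 95% confidence intervals, by the Kaplan-Meier method already planned, with events and censoring assigned to the scheduled visit. State that Kaplan-Meier is the main ulcer-free rate.
2. If the visit-based rate is kept, label it supportive, say which EGD confirms ulcer-free status, and give at each visit the number of subjects carried forward without an EGD.
3. Beside it, show a worst-case bound with leavers counted as not ulcer-free (69.1% at Week 52 in the base case above). It is a bound, not an estimate.
4. Do not replace the denominator by subjects examined at the visit plus those with an earlier ulcer. That is biased downwards by a similar amount (88.6% against 89.9%).

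Kaplan-Meier still assumes that leaving is unrelated to ulcer risk, so reasons for leaving should be tabulated beside it. No new data are needed. The cost is slightly more analysis work, wide subgroup intervals, and possibly a slightly less favourable rate.
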